7.2 Analysis Populations

7.2.1 Screened Set

Subjects considered potential candidates for the study based on pre-screening will sign an IRB/EC approved Informed Consent Form (ICF) prior to any study activities. The Investigator or delegated study research staff may then complete the first study visit with the subject.

7.2.2 Enrolled set

Every subject that receives the study device will be considered enrolled in the study and included in the Enrolled set. If a subject has provided consent and completed screening, and for any reason does not receive the study device, the subject will not be considered enrolled in the study.

7.2.3 Software

SAS® v9.2 or above will be used to analyze the data.

CONFIDENTIAL AND PROPRIETARY

This document contains information that is confidential and proprietary to Smith & Nephew PLC and Smith & Nephew, Inc. and is intended for use only by Smith+Nephew and its manufacturer. It shall not be reproduced or copied in whole or in part, nor shall the contents be disclosed by any means without prior written permission from Smith+Nephew, nor shall anyone make any use of it that is contrary to the expressed or implied wishes of Smith+Nephew.

Statistical Analysis Plan

Post-Approval Study of the R3™ Biolox® delta Ceramic Acetabular System – United States

Number: 16-4565-10
ST: 1176
Version: 5.2, 19-JAN-2024
Page: 15 of 22

7.3 Handling of Missing, Incomplete and Repeat Data

When data are being summarized, only the non-missing values will be evaluated for computing summary statistics.

In general, partial dates will be imputed as follows:

- if only the day is missing, the first day of the month will be assumed;
- if the day and the month are missing, January 1st will be assumed;
- if a date is completely missing or unknown and the visit is not indicated on the CRF, the data will not be included in a specific time window for analysis. Note that all AEs will be included regardless of whether the date is missing or incomplete.

When subjects do not attend an in-office study visit and a telephone visit is conducted instead, the data from telephone visit will be used for analyses wherever possible.

When the patient misses the final (3 year) visit but is able to return the office at a later date, the additional mHHS and radiographic data that were not collected during the telephone visit will be collected and used for the final analyses at 3 years.

7.4 Derived Data

Not applicable.

7.5 Baseline Data

Demographic data including age, gender, race, and primary diagnosis will be obtained at the preoperative visit.

The demographic and baseline characteristics will be summarized using descriptive statistics for the Enrolled set.

7.6 Disposition Data

Patient accounting will be presented according to the recommendations in the FDA guidance entitled "Clinical Data Presentations for Orthopedic Device Applications".

- **Actual A (in window):** Hips with all data (Adverse Event/Revision Assessment, modified Harris Hip Score and radiographic evaluation) at the relevant visit, in the window time frame.

CONFIDENTIAL AND PROPRIETARY

This document contains information that is confidential and proprietary to Smith & Nephew PLC and Smith & Nephew, Inc. and is intended for use only by Smith+Nephew and its manufacturer. It shall not be reproduced or copied in whole or in part, nor shall the contents be disclosed by any means without prior written permission from Smith+Nephew, nor shall anyone make any use of it that is contrary to the expressed or implied wishes of Smith+Nephew.

Statistical Analysis Plan

Post-Approval Study of the R3™ Biolox® delta Ceramic Acetabular System – United States

Number: 16-4565-10
ST: 1176
Version: 5.2, 19-JAN-2024
Page: 16 of 22

- **Actual A:** Hips with all data (Adverse Event/Revision Assessment, modified Harris Hip Score and radiographic evaluation) at the relevant visit (includes hips with visits out of the interval window).
- **Actual B:** Hips who returned to the office with any data (Adverse Event/Revision Assessment, modified Harris Hip Score or radiographic evaluation) at the relevant visit.
- **Actual Modified B:** Hips with any data (Adverse Event/Revision Assessment, modified Harris Hip Score, radiographic evaluation, or telephone visit) at the relevant visit, including hips unable to return for follow-up visits that were contacted by telephone for determination of patient satisfaction and device survival.
- **Theoretical:** Number of hips that would have reached the beginning of the study window associated with each visit if all subjects returned.
- **Deaths:** Cumulative number of subjects that died during or prior to the upper window limit of the study visit.
- **Failures:** Cumulative number of hips that failed (revision) during or prior to the upper window limit of the study visit.
- **Expected:** Theoretical hips minus the number of deaths and revisions.
- **Follow-up Rate:** Actual/Expected*100

Patients discontinued from the study prematurely will be presented, with a breakdown of the reasons for discontinuation as reported in the CRF.

Due to subject visit restrictions associated with COVID-19 pandemic, it is expected that Protocol Deviations will occur that may affect the subject accountability rates. In particular, radiographic data and data that can only be collected at the office follow up are likely to be missing or out of window. However, the telephone survey will ensure that most of the key information needed for the primary analysis at the 3-year follow-up visit is collected. Additionally, every effort will be made to gather radiographic data and the complete HHS at a later time when an in-person visit was not completed within the 3-year window.

To present a thorough assessment of hip accountability, the following information will be included in the annual reports and final study report:

- (1) The typical accountability table that has been presented in each annual report will be presented, using the same rules for inclusion in each category (i.e. Actual^A, Actual^{Awithinwindow}, Actual^B, Actual^{Mod. B}).

CONFIDENTIAL AND PROPRIETARY

This document contains information that is confidential and proprietary to Smith & Nephew PLC and Smith & Nephew, Inc. and is intended for use only by Smith+Nephew and its manufacturer. It shall not be reproduced or copied in whole or in part, nor shall the contents be disclosed by any means without prior written permission from Smith+Nephew, nor shall anyone make any use of it that is contrary to the expressed or implied wishes of Smith+Nephew.

Statistical Analysis Plan

Post-Approval Study of the R3™ Biolox® delta Ceramic Acetabular System – United States

Number: 16-4565-10
ST: 1176
Version: 5.2, 19-JAN-2024
Page: 17 of 22

- (2) Final 3-year accountability, which will include telephone visit data (or full HHS if available) plus out-of-window radiographic data as allowable for "complete data" (Actual^Awithinwindow, and Actual^A), and telephone visit data alone as allowable for other accountability categories including Actual^B and Actual^{Mod. B}.
- (3) A listing of deviations and missed/out of window visits that result from the COVID-19 pandemic.

Screening failures and patients discontinued from the study prematurely will be presented with a breakdown of the reasons for discontinuation as reported in the CRF.

Screening and enrolment summary: For each centre/site, dates that the first subject was screened/enrolled (first subject, first visit) and the last subject completed (last subject, last visit) will be provided, duration (site, 1st enrolled – final subject exit), together with number of subjects enrolled and number of subjects completed 3 year visit. Dates of all visits will be provided in the report listings.

7.7 Protocol Deviations

A protocol deviation is an instance of failure, intentionally or unintentionally, to follow the requirements of the protocol. Protocol deviations include but are not limited to: deviations from inclusion/exclusion criteria, endpoint variable criteria, and missed study visits or visits outside the window. Protocol deviations due to COVID will be tracked.

Protocol deviations will be classified as major protocol deviation and minor protocol deviation.

Major and minor protocol deviations will be summarized.

7.8 Measurement of Treatment Compliance

Not applicable.

7.9 Multiplicity

Not applicable, no adjustments for multiplicity are planned for this study.

CONFIDENTIAL AND PROPRIETARY

This document contains information that is confidential and proprietary to Smith & Nephew PLC and Smith & Nephew, Inc. and is intended for use only by Smith+Nephew and its manufacturer. It shall not be reproduced or copied in whole or in part, nor shall the contents be disclosed by any means without prior written permission from Smith+Nephew, nor shall anyone make any use of it that is contrary to the expressed or implied wishes of Smith+Nephew.

Statistical Analysis Plan

Post-Approval Study of the R3™ Biolox® delta Ceramic Acetabular System – United States

Number: 16-4565-10
ST: 1176
Version: 5.2, 19-JAN-2024
Page: 18 of 22

7.10 Analysis of Primary Endpoint(s)

The primary endpoint is overall study success at 3 years postoperative. Success is defined the same way it was in the PMA cohort, to allow comparison. Overall success is defined as:

- No component revision,
- Modified Harris Hip Score (mHHS) of at least 80 points, and
- No radiographic failure, defined as:

No radiolucencies greater than 2 mm in 50% or more in any of the cup or stem zones, no femoral or acetabular subsidence greater than or equal to 5 mm from baseline, and no acetabular cup inclination changes greater than 4 degrees from baseline when accompanied by "Mild", "Moderate", "Marked" or "Disabled" mHHS pain score.

All subjects in the enrolled population with evaluable data at 3 years postoperative will be considered for analysis. Subjects lost to follow up due to revision at any point up to the end of the three-year visit window will be considered as failures.

A one-sided analysis using the exact binomial model will be used to analyze success rate against the success rate of the PMA cohort of 86.4%, with 8% margin (as per Sample Size Section 6.1).

As mentioned in Section 7.14 additional analyses will be performed to accommodate inclusion of as many study subjects as possible in the analysis.

7.11 Analysis of Secondary Endpoint(s)

Secondary endpoints include clinical assessments of pain and function using the modified Harris Hip Score, radiographic findings, and implant survivorship. These assessments will be summarized using descriptive statistics at postoperative visits. No analyses are planned.

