7.3. Conditions for Study Termination

All reasonable efforts should be made to retain the subjects for the 3 year duration of this study. If the subject has a revision of any component the subject will be terminated from the study.

A. Screening Failure

If a subject has provided consent, completed screening, and for any reason does not receive the study device, the subject will not be considered enrolled in the study. For these subjects an End of Study: Subject Disposition form needs to be completed and submitted to the Sponsor. Pre-operative, operative, and discharge forms do not need to be submitted.

B. Voluntary Withdrawal

Study participation is voluntary, and subjects may withdraw at any point during the study without giving their reason for doing so. An End of Study: Subject Disposition form will be completed for all subjects who do not finish the study, to document the reason for the withdrawal in the CRF.

C. Lost to Follow-Up

Some actively enrolled subjects will not return for follow-up exams due to a variety of reasons. Study personnel must make a reasonable effort to contact the subject and document the following contact attempts prior to declaring a subject to be lost to follow-up: the subject has been contacted according to the sites policies, but no less than 2 documented phone contacts and 1 certified letter without response. Copies of all attempts to reach the subjects per regular mail or email and/or the attempts to contact the subject via other means should be documented, and that documentation should be kept with the subjects CRFs. A subject will be considered lost to follow-up if he/she does not appear for the scheduled study visit for 2 consecutive visits and study personnel are unable to contact the subject.

D. Study Termination by Investigator/Sponsor

The Investigator **may** withdraw subjects from the study for many reasons, including but not limited to the following:

- subject noncompliance to study schematic

Smith & Nephew - Advanced Surgical Devices Division

Post-Approval Study of the R3™ Biolox® delta Ceramic Acetabular System – United States	Number: 16-4565-10
	Version 6.0
	Page: 17 of 28

- subject lost to follow-up

The Investigator **should** withdraw subjects from the study:

- in case any component of the original hardware is revised/exchanged
- the Investigator or the Sponsor stops the study for any reason

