6 STATISTICAL CONSIDERATIONS

6.1 Determination of Sample Size

The primary objective of this study is to confirm that the safety and effectiveness of the R3 Biolox delta Ceramic Acetabular System in the US population is consistent with the effectiveness and safety profile shown in the European study (PMA cohort). The primary endpoint is overall study success at 3 years postoperative. Secondary endpoints include clinical assessments of pain and function, radiographic findings, and implant survivorship.

Overall success (as defined in the section entitled "Primary endpoint") in the PMA Cohort was found to be 86.4% at 3 years postoperative for the Biolox delta ceramic-on-ceramic (DOD) treatment group. It is expected that the overall success for the DOD US Cohort is similar to the overall success for the DOD PMA Cohort (European data).

Statistical Hypotheses:

$$H_0: \pi_{DOD} - 0.864 \leq \delta$$

$$H_a: \pi_{DOD} - 0.864 > \delta$$

Where,

π_{DOD} = Overall Success of DOD US

1-sided alpha error = 5%

Power of the test = 80%

$\delta = -0.08$

The minimum sample size required for hypothesis testing: 146 DOD US subjects. The total sample size after adjustment for lost-to-follow-up (20%) is 183 DOD subjects. Sample size was calculated assuming use of an Exact Binomial test³.

³ https://support.sas.com/documentation/cdl/en/statug/63962/HTML/default/viewer.htm#statug_power_a0000000996.htm

CONFIDENTIAL AND PROPRIETARY

This document contains information that is confidential and proprietary to Smith & Nephew PLC and Smith & Nephew, Inc. and is intended for use only by Smith+Nephew and its manufacturer. It shall not be reproduced or copied in whole or in part, nor shall the contents be disclosed by any means without prior written permission from Smith+Nephew, nor shall anyone make any use of it that is contrary to the expressed or implied wishes of Smith+Nephew.

Statistical Analysis Plan

Post-Approval Study of the R3™ Biolox® delta Ceramic Acetabular System – United States

Number: 16-4565-10
ST: 1176
Version: 5.2, 19-JAN-2024
Page: 14 of 22

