7 STATISTICAL ANALYSIS

7.1 General

Categorical variables will be summarized with the number and percent of subjects in each group. Continuous variables will be summarized with the mean, standard deviation, median, minimum, and maximum values. 95% confidence intervals will be calculated for the primary and secondary endpoints.

All data collected in the CRF will be presented in the listings.

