7.13 Analysis of Safety Endpoint(s)

The number of AEs, SAEs, USADEs, Reoperation and Revisions, and the number and the percentage of patients experiencing AEs, SAEs, USADEs will be presented for the enrolled set.

The number of AEs and the number and the percentage of patients with at least one AE will be presented for AEs and SAEs.

The number and the percentage of patients with at least one AE will be presented by severity, seriousness, device relatedness and procedure relatedness.

Adverse event definitions are shown below and are as per the study protocol.

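### SAP 7.11 sets no failure rule, censoring rule or interval for implant survivorship; use Kaplan-Meier at 36 months plus the cumulative revision proportion

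*SAP*

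**What the plan says.** SAP 5.2 and Protocol 2.2 name implant survivorship as a secondary endpoint. On method, SAP 7.11 says only: "These assessments will be summarized using descriptive statistics at postoperative visits. No analyses are planned". SAP 7.1 nevertheless promises that "95% confidence intervals will be calculated for the primary and secondary endpoints", and Protocol 9.1 promises the same.

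Four other provisions bear on it:

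- **Protocol 7.3:** "If the subject has a revision of any component the subject will be terminated from the study".
- **SAP 7.3:** "only the non-missing values will be evaluated for computing summary statistics".
- **SAP 7.10**, for the primary endpoint only: "Subjects lost to follow up due to revision at any point up to the end of the three-year visit window" are failures.
- **SAP 7.6**, for patient accounting only, defines failures as "Cumulative number of hips that failed (revision) during or prior to the upper window limit of the study visit".

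SAP 7.13 also lists "The number of AEs, SAEs, USADEs, Reoperation and Revisions" for the Enrolled set. On planned loss, SAP 6.1 says: "The total sample size after adjustment for lost-to-follow-up (20%) is 183 DOD subjects".

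No section gives survivorship a time origin, an event, a censoring date, a denominator, an estimator or an interval method.

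**The concern.** Survivorship is a time-to-event quantity, and the subjects who carry the failures stop contributing visits once they fail. If device status is summarised at each visit among those with data, a hip revised at month 12 is absent from the 2-year and 3-year summaries. Survivorship could then read close to 100% in the same report that lists revisions under SAP 7.6 and 7.13. The promised 95% interval also has no stated denominator, so two programmers could follow the text and produce different intervals.

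The study exists to confirm that US results are consistent with the European PMA cohort. Survivorship is the secondary endpoint that speaks most directly to device failure, so an internally inconsistent figure would be hard to defend.

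**Working it through.** **Inputs from the documents.** 183 enrolled, 146 evaluable, 20% loss (SAP 6.1). The 3-year visit is at 36 ± 2 months, so months 34 to 38 (SAP 3.2.3).

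**The plan's own figure.** An exact one-sample binomial test of 0.864 − 0.08 = 0.784 against 0.864, one-sided 5%, first reaches 80% power at n = 146 (reject at 123 or more successes; alpha 0.0492; power 81.2%). Then 146/0.80 = 182.5, rounded up to 183. Both stated numbers reproduce. The documents state no survivorship figure to reproduce.

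**Assumptions.** The documents give no revision count or timing. I took one hip per subject; *r* = 2, 4 or 6 revisions spread evenly over months 2.4 to 31.2; 37 − *r* losses spread evenly over months 1.2 to 33.9; and 146 subjects leaving evenly over months 34 to 38.

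**Kaplan-Meier.** S(t) = Π(1 − 1/nᵢ), where nᵢ is the number at risk at each revision. For *r* = 4 the numbers at risk are 181, 171, 161 and 150:

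S(36) = (180/181)(170/171)(160/161)(149/150) = 0.9760.

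For the log-log interval, Σ1/[nᵢ(nᵢ − 1)] = 0.0001487, its square root is 0.01219, and 0.01219/|ln 0.9760| = 0.501. The limits S^exp(±1.96 × 0.501) are 0.937 and 0.991.

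| Revisions | KM at 36 months (95% CI) | 1 − r/183 | 146/(146 + r) (exact 95% CI) | Attendees only |
|---|---|---|---|---|
| 2 | 98.8% (95.2–99.7) | 98.9% | 98.6% (95.2–99.8) | 100% |
| 4 | 97.6% (93.7–99.1) | 97.8% | 97.3% (93.3–99.3) | 100% |
| 6 | 96.4% (92.2–98.4) | 96.7% | 96.1% (91.6–98.5) | 100% |

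The largest gap among the three methods that count revisions is 0.9672 − 0.9605 = 0.0067, or 0.7 points. The gap to the attendees-only figure is 1.2 to 3.6 points for Kaplan-Meier. When no revision falls in months 34 to 38, the failure rule matters much more than the choice of estimator.

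**A revision inside the 3-year window.** Keep four revisions, at months 2.4, 12 and 21.6, and move only the last. At 36 months Kaplan-Meier has three events: (180/181)(170/171)(160/161) = 0.9825. At 38 months:

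| Last revision | At risk | KM at 38 months (95% CI) |
|---|---|---|
| month 37 | 38 | 0.9825 × 37/38 = 95.7% (85.5–98.8) |
| month 37.5 | 20 | 0.9825 × 19/20 = 93.3% (73.7–98.5) |
| month 37.9 | 5 | 0.9825 × 4/5 = 78.6% (22.6–96.2) |

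The counts do not move: 1 − 4/183 = 97.8% and 146/150 = 97.3%. The 38-month estimate is therefore unstable, because the risk set falls from 146 at month 34 to 73 at month 36 and then empties. The 36-month estimate is stable but omits the late revision (98.3% against 97.3% by 146/150), so the cumulative proportion has to stand beside it.

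**No revisions.** Kaplan-Meier gives 100% with no usable log-log interval. The exact lower limit on 146 hips of known status is 0.025^(1/146) = 97.5%.

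**The case against.** The strongest reply is that SAP 7.6 already gives a cumulative, visit-by-visit count of revised hips, which is one fair reading of a descriptive by-visit summary. Revisions have their own form (Protocol 8.1 G), must be reported to the sponsor (Protocol 8.3) and appear again under SAP 7.13. A revised hip's status is known, so it need not be treated as missing.

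Most of this stands. A reader might infer that the plan will report 100% survivorship, or that revisions will go unreported; the documents support neither. The attendees-only figure is one reading that the text permits, not one that it requires. Nor is the primary result biased in this way, because SAP 7.10 counts revised subjects as failures.

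What the reply does not supply is the link. SAP 7.6 serves accounting and 7.10 serves the primary endpoint; nothing applies either rule to survivorship or gives a denominator for the promised interval.

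A reader might also infer that Kaplan-Meier should run to 38 months so as to match the 7.6 and 7.10 counts. It would not match them: with a revision at month 37 it gives 95.7%, against 97.8% and 97.3% by count. Nor do methods that count revisions always agree within 0.7 points; that bound fails once a revision falls in months 34 to 38.

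**Conclusion.** The gap is real and worth closing, at moderate weight. SAP 7.11 lets a by-visit survivorship summary leave out earlier revisions and gives no basis for the interval promised in SAP 7.1. In the illustration the omission is worth 1.2 to 3.6 points for 2 to 6 revisions among 183. The sample size and primary test do not change.

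These sizes rest on assumed revision numbers and timing, even spacing of losses and exits, one hip per subject, and loss unrelated to revision.

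**What to change.** In SAP 7.11:

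1. Estimate freedom from revision of any component by Kaplan-Meier in the Enrolled set, from implantation. Every revision is an event; censor at death or at last known device status, by office visit or telephone.
2. State whether the unit is the hip or the subject, consistent with SAP 7.6, which counts failures by hip but deaths by subject.
3. Report the 36-month estimate with a log-log 95% interval, and the number at risk at each visit and at 36 months. Do not headline the 38-month estimate.
4. Alongside it, whatever the data show, report cumulative revisions to the end of the 3-year window (the SAP 7.6 failures) as a proportion with an exact 95% interval. The denominator is hips revised plus hips with device status known at the 3-year contact. This also covers the case of no revisions.
5. Replace the statement that no analyses are planned with one that no hypothesis tests are planned.
6. Label the estimator as added after data collection, which the Protocol Synopsis says was complete by May 2023.

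The cost is SAP wording and a little more analysis work, with no new visits or assessments. It assumes that the date of telephone contact was recorded. Kaplan-Meier assumes that loss is unrelated to revision. The proportion leans slightly towards lower survivorship, because it keeps every known revision but drops unrevised hips that were lost.
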